### 3.6.6 Completed study

The end of the study is defined as the date the last subject completes the Follow-up Phone Call.

### 3.6.7 Procedure after the completion of the study

When the study is completed and the site has been closed out, the Investigator will be asked to notify the governing IRB of study closure.

## 4 SUBJECT INCLUSION AND EXCLUSION CRITERIA

Subjects must meet all of the following inclusion criteria to be eligible for participation in this study. On criteria that involve the eyes, both eyes must qualify.

### 4.1 Subject inclusion criteria

1. Male or female aged 10 years or less (pre-pubescent with no childbearing potential)
2. Capable of undergoing an eye exam per investigator judgement
3. Subject's legally appointed and authorized representative willing to sign and date an informed consent form (ICF) and, where appropriate, the subject willing to sign an assent form prior to any study-related procedures being performed.
4. Parent/legal guardian and subject are willing and able to follow instructions and can be present for the required study visits and Follow-up Phone Call for the duration of the study.
5. Have a healthy, normal cornea.
6. Have a planned ophthalmic examination.

### 4.2 Subject exclusion criteria

Subjects who meet any of the following exclusion criteria are ineligible for this study:

1. Have participated in an investigational study (drug or device) within the past 30 days.

2. Have a known contraindication to local anesthetics, Septocaine®, any component of the Investigational Medical Product (IMP) or Proparacaine HCl Ophthalmic Solution.
3. Children with known autism spectrum disorders or known to have heightened sensitivity.
4. Corneal pathology that would make the corneal sensitivity lower/higher or make the test hard to perform or interpret (e.g., central corneal scar, clinically apparent corneal edema, etc.).
5. Have low visual acuity  
(Optotype capable): Corrected acuity in either eye worse than 20/200 Snellen (0.1 ETDRS) or equivalent  
(Not optotype capable): No demonstrable reaction to light.
6. Manifest nystagmus
7. Have had ocular surgery (intraocular, refractive, extraocular muscles, eyelid) or general surgery in either eye within the past 45 days (Note: dental restorative work allowed).
8. Have had an intravitreal injection in either eye within 14 days of randomization.
9. Have ocular surface disease requiring punctal plugs, or evidence of current ocular inflammation.
10. Subject who must wear contact lenses on Study Day 1 (Visit 2).
11. Are currently using, or used within the past 7 days, a systemic or topical Non-steroidal Anti-Inflammatory Drug (NSAID).
12. Are currently using, or used within the past 30 days, a systemic opioid or opiate analgesic.
13. The subject's parent(s) or legal guardian(s) is a study team member (i.e., has direct involvement in this study or other studies under the direction of the Investigator or the study center) or is a family member of either the Investigator or other team members.

#### **4.3 Subject replacement**

This study will enroll up to 70 subjects in order to obtain at least 60 evaluable subjects. No replacement of withdrawn subjects is allowed.

## **5 TREATMENT OF SUBJECTS**

Subjects will receive a single dose (two drops) of IMP in one (study) eye. The IMP will be randomized as either AG-920 or Proparacaine HCl Ophthalmic Solution. The study eye will be randomized as either right eye (OD) or left eye (OS). The single dose will be administered by the clinic staff.

### **5.1 Concomitant medications**

#### **5.1.1 Prohibited medications**

The list of prohibited medications provided below may not be comprehensive. Investigators are encouraged to consult with the Medical Monitor for a decision about proceeding if they have any questions or concerns about any medication.

The following medications are prohibited.

- [REDACTED]

- [REDACTED]

- [REDACTED]

As noted in the exclusion criteria (Section 4.2), individuals must refrain from contact lens wear on the Dosing and Eye Exam Day (Day 1).

#### 5.1.2 Allowed medications

Other than the agents and/or times noted above, systemic therapy with agents is allowed.

Use of all medications should be documented on the appropriate CRF. Investigators are encouraged to contact the study monitor for escalation to the Medical Monitor (if necessary) for any questions regarding allowed medications. Judgment of continued study participation by the subject, and inclusion of this subject's subsequent visits in the safety and efficacy analysis will be made by the Sponsor.

All medications which the subject has taken within 30 days prior to screening and during the study will be recorded in the CRF. The name of the drug, dose, route of administration, duration of treatment and indication will be recorded for each medication if known. For combination products (e.g., Contac®), the brand name is required. For non-combination products, the generic name is desired. The use of routine ophthalmic diagnostic pharmaceutical agents (e.g., fluorescein and local anesthetic) will be allowed, and individual documentation not required.

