### 3.5 Randomization and procedure for breaking the code

A randomization code for allocating the treatments and study eye will be prepared by an independent biostatistician, who is not involved in the day-to-day conduct of the study. Subjects

will be randomized in a 1:1 ratio to receive AG-920 or Proparacaine HCl Ophthalmic Solution. The site will have a randomization list that will assign each subject to treatment and study eye.

The study is single masked. Treatment assignments will be masked to the subjects and their parent/legal guardian only so there is no reason to break the code.

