### 9.3 *Analysis populations*

Randomized Population: The randomized population will include all subjects who were randomized to treatment. Baseline (screening) variables and demographic characteristics will be summarized for this population.

Intent-to-Treat Population (ITT): The ITT population will include all randomized subjects who have received at least one dose (two drops) of study medication. This population will be the primary population for the efficacy analyses and all efficacy variables will be summarized using this set of subjects. The ITT population will include subjects as randomized.

Per-protocol population (PP): The PP population is a subset of the ITT population, which will include those subjects (and their visits) who do not have major protocol violations likely to seriously affect the primary outcome of the study as judged by a masked evaluation prior to the unmasking of the study treatment. This population will be the secondary population for efficacy analyses and all efficacy variables will be summarized using this set of subjects. If the PP and ITT populations are exactly the same and there are no missing data, then additional efficacy analyses on the PP population will not be performed. The PP population will include subjects as treated.

Safety Population: The safety population will include all randomized subjects who have received at least one drop of study medication. This population will be used to summarize the safety variables and will summarize subjects as treated.

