##### Intention-to-treat (ITT) Population

This population is defined as all subjects who are randomized to treatment and have received at least one dose (2 drops) of the study medication. The ITT population is the primary population for efficacy evaluation in this study. Treatment identification is defined in the ITT population by treatment assignment. The ITT population will be identified and finalized before the database is locked and the treatment assignment is merged into the study database.

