##### Per-Protocol (PP) Population

This population is defined as a sub-population of the ITT population. The PP population is the secondary population for efficacy evaluation in this study and will be defined as all randomized subjects who completed the study treatment with no major protocol violations likely to seriously affect the primary outcome of the study as judged by the investigator. In case there is a difference between treatment assigned and received, treatment actually received will be utilized to define the treatment identification in the PP population. In case there are missing data in efficacy measures, the analysis of the PP population will be based on observed or actual data only (without imputation). The PP population will be identified and finalized before the database is locked.

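### Protocol 5.1.2 lets the Sponsor judge whether a child's later visits enter the analyses after medication use, which contradicts the ITT and Safety definitions, with no order of precedence

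*Protocol*

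**What the plan says.** Protocol 5.1.2 (Allowed medications) assigns two judgments to the Sponsor when medication questions arise: whether the child continues, and whether later data are analysed. On the second it says "inclusion of this subject's subsequent visits in the safety and efficacy analysis will be made by the Sponsor". The visible text gives no criteria, no deadline, no masking condition and no restriction to a particular analysis set.

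The population definitions contain no such discretion:

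- Safety, Protocol 9.3: "The safety population will include all randomized subjects who have received at least one drop of study medication". SAP 3.1 has the same rule.
- ITT, Protocol 9.3: "The ITT population will include all randomized subjects who have received at least one dose (two drops) of study medication". SAP 3.1 likewise takes "all subjects who are randomized to treatment and have received at least one dose (2 drops) of the study medication".
- PP is the only set that allows exclusion for violations. Protocol 9.3 has these "as judged by a masked evaluation prior to the unmasking of the study treatment", whereas SAP 3.1 requires "no major protocol violations likely to seriously affect the primary outcome of the study as judged by the investigator".

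On masking, Protocol 3.5 says "Treatment assignments will be masked to the subjects and their parent/legal guardian only so there is no reason to break the code". The same section gives the site the randomization list.

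Two passages limit the timing of exclusions. Protocol 9.4.5 has important deviations documented before unmasking. SAP 3.1 has the ITT population finalized before database lock and before treatment assignment is merged in.

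**The concern.** A fixed analysis set protects the comparison because nobody can choose who is counted after seeing what happened. Section 5.1.2 opens a way round that. A child who was randomized and fully dosed belongs in both ITT and Safety under Protocol 9.3, yet under 5.1.2 the Sponsor could withhold that child's later visits from both analyses.

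Two things are at stake. For efficacy, the arms are small (about 30 evaluable children each) and the endpoint is a single yes/no answer, so one child can matter to a borderline claim. For safety, the clause expressly reaches the safety analysis, and medication use is not a reason to leave out what happened to a dosed child.

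**Working it through.** **1. The rules side by side**

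| Question | Protocol 5.1.2 | Protocol 9.3 / SAP 3.1 |
|---|---|---|
| What decides inclusion in ITT and Safety? | Sponsor judgment | Randomization and drops received |
| Exception for medication use? | Yes, for later visits | None |
| Unit removed | Visits | Children (in PP, Protocol 9.3 also mentions their visits) |
| Cross-reference to the other rule? | None | None |

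Both cannot be followed for a dosed child whose later visits the Sponsor withholds, and no precedence is stated.

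**2. Do the timing safeguards close the gap?**

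- Protocol 9.4.5 concerns important protocol deviations. Section 5.1.2 concerns allowed medications, whose use need not be a deviation.
- SAP 3.1 fixes ITT membership before treatment is merged. Section 5.1.2 removes visits, so a child could stay in ITT without the visit that carries the endpoint.
- Pre-merge timing protects less where the site knows the assignment and the investigator makes the efficacy reading.

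They are partial safeguards.

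**3. Which data are exposed?** Screening can precede Visit 2 by up to 3 days (Protocol 6.4). If so, Visit 2 is a later visit, and it holds the only efficacy reading. But Protocol 6.4.1 repeats the eligibility and medication review before dosing, and 6.4.2 randomizes only after qualification is confirmed. A child stopped at that point has no arm and no outcome. The efficacy route therefore needs pre-dose medication that comes to light only after dosing. Medication taken after the exam cannot affect a reading made 2-4 minutes after the last drop; there, only later safety data are open, such as the phone call or an unscheduled visit.

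**4. Size.** The documents give no response rates, so there is no figure of the plan's to reproduce, and all counts below are assumptions. About 30 per arm comes from the Protocol Summary; the 90% interval and the 20% rule come from SAP 2.9.1. One child is 1/30 = 3.3 points of an arm.

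Lower limit = d - t(0.95, df) × √[s²(1/n₁ + 1/n₂)], where d = p₁ - p₂, s² = [n₁p₁(1-p₁) + n₂p₂(1-p₂)]/df and df = n₁ + n₂ - 2.

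- 26/30 vs 29/30: d = -10.0 points; s² = 4.4333/58 = 0.07644; SE = 7.14 points; t = 1.672; limit = **-21.9**.
- One AG-920 non-responder removed, 26/29 vs 29/30: d = -7.0 points; s² = 3.6563/57 = 0.06415; SE = 6.60 points; t = 1.672; limit = **-18.0**.

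With df = N - 3, as in the SAP model with eye side (its sum of squares ignored), the limits are -22.0 and -18.1. The rule flips whether 20% means 20 points or 20% of the reference rate (0.20 × 29/30 = 19.3 points).

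The P > 0.05 rule (Pearson chi-square, uncorrected) does not flip here: p is about 0.16 before and 0.28 after. It does flip at 26/30 vs 30/30, from 0.038 to 0.071 with 26/29.

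Counts where the 20% rule does not change (df = N - 3):

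- 33/35 vs 34/35: -11.1 becomes -7.0; passes both times.
- 28/35 vs 34/35: -29.6 becomes -26.8; fails both times.

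**The case against.** Several counter-arguments have force.

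- *A reader might infer that 5.1.2 overrides the population definitions.* The documents do not say so. The SAP restates the definitions without the discretion, so this is an unreconciled contradiction.
- *A reader might infer that the Sponsor is unmasked when it decides.* That follows only from the statement that masking covers the child and family. Nothing says the Sponsor sees arm or outcome at that moment, and nothing prevents it. The timing safeguards count against the stronger reading, though they do not clearly cover removal of visits.
- *A reader might treat Visit 2 as the only post-dose collection of adverse events.* It is not: Protocol 6.4.4 also asks about them at the phone call. Protocol 3.6.1 lists that call separately from the visits, so it is arguable whether 5.1.2 reaches it.
- *The numerical example may use the wrong mechanism.* SAP 2.8 counts efficacy values missing through invalid data or early termination as NO, so a failed child would stay a failure and 26/30 would stand. This is a fair limit, but not a full answer: the same section ends by treating missing data as missing, and scoring a withheld responder as NO would also move the result. Neither document says how a withheld visit is handled.
- *The counts are chosen near the boundary.* True, as the unchanged cases show.
- *Criteria may lie in the blacked-out list of prohibited medications in Protocol 5.1.1.* That cannot be checked. The visible clause in 5.1.2 sets none for inclusion in the analysis.

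**Conclusion.** The contradiction stands. The Sponsor has an unconditioned judgment over inclusion of visits in both analyses, while ITT and Safety admit no such judgment. The efficacy exposure is narrow, mainly pre-dose medication use discovered after dosing; the remaining exposure is to later safety data. In a borderline result one removal could decide the equivalence claim (-21.9 to -18.0 points), provided that the counts are near those assumed and the child leaves the denominator. In many configurations it would change nothing. The documents do not show that the Sponsor would decide with knowledge of arm or outcome. The change is worth making because the route to post-randomization exclusion is real and closing it costs almost nothing.

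**What to change.** Delete the clause on inclusion in the analysis from Protocol 5.1.2. If no amendment is planned, add a sentence to SAP 3.1 that expressly prevails over it. Either way, state that medication use never removes a child or a visit from the ITT or Safety analyses, and can affect only the PP set, through the masked review in Protocol 9.3, completed before database lock.

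That remedy depends on the PP review being masked. SAP 3.1 currently gives the PP judgment to the investigator, whom the protocol does not mask, so amend it to match Protocol 9.3.

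The cost is one sentence in the next amendment or in the SAP, plus a one-line correction to the PP definition. No data collection changes. The Sponsor gives up only its discretion over what is analysed; its judgment on continued participation is not touched.

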#### 5.2 Female Subjects

As all subjects are pre-pubescent, typical language regarding women of childbearing potential is not required.

## 6 STUDY PROCEDURES

### 6.1 General Procedures:

The study will consist of 1 or 2 clinic visits and 1 Follow-up Phone Call. All ocular assessments will be performed on both eyes. Subjects will be screened for entry (Visit 1) and randomized/treated (Visit 2). Visit 1 and 2 may be on the same day. At randomization, subjects will receive a single dose of IMP in the study eye and have an eye exam 2-4 minutes post the end of their IMP dose. The PI will assess if they were able to conduct the eye exam or not. Subjects and/or parent/legal guardians will then have a safety Follow-up Phone Call 1-4 days (Days 2-5) following Visit 2.

### 6.2 Re-screening Procedures:

A subject who is first designated as a screen failure prior to being randomized will be allowed to rescreen one additional time 7-30 days after initial screening.

### 6.3 Visit 1 (Screening) – Day -2 to 0/1

Visit 1 may be combined with Visit 2 in order to accommodate clinic logistics. If both visits are combined, Visit 1 will last anywhere from 1-2 hours. Topical anesthetic drops may cause a mild stinging or burning sensation upon instillation.

The following procedures will be performed in the following suggested order at Visit 1. All ocular tests at this and all visits will be performed in both eyes:

- Obtain written informed consent from parent/legal guardian, and, where appropriate, written assent from the subject, to participate before any study-required procedures have been conducted
- Collect demographics (sex, year of birth, race, ethnicity, iris color)
- Collect systemic medical history and ocular medical history
- Review of prior and concomitant medications (including ocular medications)
- Measure Visual Acuity (VA) [REDACTED]
- Perform external eye exam
- Verify subject eligibility based on Inclusion/Exclusion requirements
- Schedule subject to return for Visit 2 if Visit 1 and 2 are not performed on the same day.

#### 6.4 Visit 2 (Randomization/Treatment) – Day 1

Visit 2 must occur within 3 days of Visit 1 (Screening) if it is not performed on the same day as Visit 1. As noted in Section 6.3, Visit 1 and Visit 2 may be performed on the same day for clinic logistics. At Visit 2, subjects are expected to be in the clinic for up to 60 minutes post dose for observation.

##### 6.4.1 Pre-dose

The following procedures will be performed in the following order at Visit 2, if Visit 1 was not performed on the same day:

- Re-verify subject eligibility based on Inclusion/Exclusion requirements.
- Review of any changes in health (medical history and AEs) or concomitant medications (including ocular medications)

##### 6.4.2 IMP Treatment

- Once qualification is confirmed, subject will be randomized.
  - Subject will be randomly assigned to receive a single dose of either AG-920 or Proparacaine HCl Ophthalmic Solution
  - Subject will be randomly assigned to receive the IMP dose into one eye (OD or OS) only (study eye)
  - Subjects and parent/legal guardian should be reminded that instillation of study drug, like other topical anesthetic drops, may cause a mild stinging or burning sensation upon instillation.
- Retrieve IMP kit number assigned and confirm study eye.
- For AG-920:
  - [REDACTED]
  - Administer 1 drop of IMP to the study eye
    - Wait 30 seconds
    - Administer a second drop of IMP to the same study eye from the same vial

- [REDACTED]
- For Proparacaine:
  - Remove dropper bottle from kit (carton)
  - Open bottle top
  - Administer 1 drop of IMP to the study eye
  - Wait 30 seconds
  - Administer a second drop of IMP to the same study eye from the same vial
  - Recap bottle and retain used bottle in the carton (kit) for accountability
- Assess for adverse events

### 6.4.3 Post Treatment and Eye Exam

#### 6.4.3.1 2-4 minutes Post Treatment

- At the 2-4 minutes time point (after the last drop of study drug is administered), the eye exam for which the subject is seeing the ophthalmologist will be conducted.
- PI is queried [REDACTED]

#### 6.4.3.2 15-60 minutes Post Treatment

Fifteen (15) to 60 minutes after the eye exam, the following examinations will be performed

- Visual Acuity
- External eye exam
- Slit lamp biomicroscopy ONLY if necessary for a suspected AE
- Assess for adverse events and changes in medications
- Schedule Follow-up Phone Call between Days 2-5 (1-4 days following dosing).

*Windows: Times will be measured to the nearest minute*

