### 2.2 Description of Trial Design

This is a Phase 3, randomized, active-controlled, single-masked, parallel-group study of safety and anesthetic efficacy of AG-920 topical drop versus Proparacaine HCl Ophthalmic Solution (Proparacaine) in healthy pediatric subjects. The study will evaluate the safety and anesthetic efficacy following one dose of Articaine Sterile Topical Ophthalmic Solution (AG-920), in comparison with Proparacaine (active-control). Eligible subjects will be randomized in a 1:1 ratio to receive a single dose of AG-920 or active-control into one eye, designated as subject's study eye. The application of one single dose of AG-920 or active control involves two drops of the study medication 30 seconds apart into the subject's study eye.

The study consists of two visits and a follow-up phone call: one screening visit on Day -2 (Visit 1), one baseline/assessment visit on Day 1 (Visit 2), and one follow-up phone assessment on Day 2-5 (Phone Follow-Up). The screening visit and baseline/assessment visit may be conducted on a single day.

Following the screening visit, eligible subjects will return to the clinic on Day 1 to have their study eye randomly assigned (right eye=OD or left eye=OS) and to be randomized to receive the study medication into the study eye. Two to four minutes post the end of their dose (following second drop), subjects will undergo an eye exam for which the subject is seeing the ophthalmologist and the principal investigator (PI) will assess if they were able to conduct the eye exam or not. Dosing of the study medication and eye exam will be performed by the PI.

To assess the anesthetic effect of the study medication, PI will be queried if the subject has achieved adequate anesthesia for the PI to conduct the eye exam at 2 to 4 minutes post dose application by answering Yes or No. 15 to 60 minutes post dose application, the following eye exam or tests will be performed by the PI: visual acuity and external eye exam and, if needed, a slit lamp bio-microscopy test.

All subjects who are randomized and who receive a single dose of either AG-920 or Proparacaine HCl Ophthalmic Solution on Day 1 will be followed up with a phone call on Day 2-5 (1-4 days post treatment) for safety assessment.

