#### Visual Acuity and External Eye Exam

Age-appropriate visual acuity tests and external eye exam will be summarized for abnormality by treatment for the screening (pre-dose) and Day 1 (post-dose), using frequency and percent. The analysis will be based on the safety population defined in [Section 3.1](#).

Where applicable, for both study eye and fellow eye, abnormal findings of visual acuity and external eye exam at screening and post-dose will be analyzed, respectively, for differences between AG-920 and active-control groups, using a Chi-square test.

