## 5.4 Visual Acuity and External Eye Exam

Frequency and percent of visual acuity abnormality will be presented by treatment for the pre-dose (screening) and post-dose assessments in [Table 5.1.1](#) for the study eye.

Frequency and percent of visual acuity abnormality will be presented by treatment for the pre-dose (screening) and post-dose assessments in [Table 5.1.2](#) for the fellow eye.

Frequency and percent of eye exam abnormality will be presented by treatment for each category of iris, pupil, and lens at the pre-dose (screening) and post-dose assessments in [Table 5.2.1](#) for the study eye.

Frequency and percent of eye exam abnormality will be presented by treatment for each category of iris, pupil, and lens at the pre-dose (screening) and post-dose assessments in [Table 5.2.1](#) for the fellow eye.

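### Post-dose acuity and external eye findings follow an eye exam whose diagnostic drops need no individual record, so abnormal findings may not be attributable to study drug

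*Protocol*

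**What the plan says.** **Order of events.** At 2 to 4 minutes after the last drop, "the eye exam for which the subject is seeing the ophthalmologist will be conducted" (Protocol 6.4.3.1). The visible text does not fix what that exam contains. Visual acuity and the external eye exam come next: "Fifteen (15) to 60 minutes after the eye exam, the following examinations will be performed" (Protocol 6.4.3.2; Table 1 agrees). No later ocular examination is scheduled, because Day 2-5 is a phone call.

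**Drops given in that exam.** Protocol 5.1.2 states: "The use of routine ophthalmic diagnostic pharmaceutical agents (e.g., fluorescein and local anesthetic) will be allowed, and individual documentation not required". Section 5.1.1 opens its list with "The following medications are prohibited", but the items are redacted.

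**Use of the findings.** SAP 5.4: "Frequency and percent of eye exam abnormality will be presented by treatment for each category of iris, pupil, and lens", before and after dosing, for the study eye and the fellow eye; acuity abnormality is treated likewise. SAP 2.9.3 adds that "abnormal findings of visual acuity and external eye exam at screening and post-dose will be analyzed" for differences between the arms by chi-square test. Neither section flags or separates a finding that follows a diagnostic drop.

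**Time anchor.** SAP 2.2 counts the same checks from dosing: "15 to 60 minutes post dose application, the following eye exam or tests will be performed by the PI". Protocol 6.4 says "subjects are expected to be in the clinic for up to 60 minutes post dose for observation".

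**The concern.** Safety and tolerability is the only secondary objective, and the subjects are healthy children for whom Protocol 1.2 anticipates no personal benefit. The scheduled post-dose examinations should therefore describe what the study drug did. Instead they are made after an exam in which other drops may have been given with no line in the record.

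The waiver matters even if only the named agents are used. Local anesthetic is the class to which both study products belong, and Protocol 1.2 lists stinging or burning and redness among the expected effects of both. An extra unlogged anesthetic drop could cause the same complaint as the study drop. Under Protocol 8.3 any adverse event after dosing counts as treatment-emergent. Table 2 classes an event with a reasonable time relationship as related even where another drug could also explain it. Without a drop record, that attribution cannot be revisited.

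The waiver also works against the SAP's own plan. SAP 2.6.4, 2.9.4 and 5.6 call for eye-related concomitant medication after randomization to be reported by eye, and Day 1 diagnostic drops can be absent from those tables.

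**Working it through.** The documents give no figure on this point, so there is none to reproduce. The check covers the timing, the route by which a drop effect could reach a table, and an illustration of size.

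**1. Timing.** Inputs: exam 2-4 minutes after the last drop (Protocol 6.4.3.1) and checks 15-60 minutes after the exam (6.4.3.2).
- Earliest: 2 + 15 = 17 minutes after the last drop. Latest: 4 + 60 = 64 minutes. The length of the exam is added to both.
- SAP 2.2 gives 15-60 minutes after dosing, and Protocol 6.4 expects up to 60 minutes in clinic after dosing.
- The latest protocol time therefore exceeds both. The heading of 6.4.3.2 also says post treatment, while its text says after the exam.

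**2. Route into the tables.** Pupil abnormality and acuity are tabulated, so a drop that alters either would be counted. No agent of that kind is named, so this route is conditional. The surface effects of extra local anesthetic would mostly appear as adverse events, since SAP 5.4 lists only iris, pupil and lens for the external exam.

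**3. Size.** Inputs from the documents: about 30 evaluable subjects per arm, 1:1 allocation, two-sided 0.05, chi-square test. Assumptions: *d*, the share of children with a drop-induced abnormality, and a true AG-920 effect of 20% against 0%.

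Expected rates are *d* + (1 − *d*) × 0.20 on AG-920 and *d* on Proparacaine. For example, at *d* = 0.25 the AG-920 rate is 0.25 + 0.75 × 0.20 = 0.40. The probability of P < 0.05 is the sum of the binomial probabilities of all pairs of counts (x₁, x₂) for which ((x₁ − x₂)/30)² / [p̄(1 − p̄) × 2/30] exceeds 3.841, where p̄ = (x₁ + x₂)/60.

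| *d*, same in both arms | Rates if effect is real | Power | P < 0.05 with no drug effect |
|---|---|---|---|
| 0% | 20% vs 0% | 88% | 0% (no events) |
| 25% | 40% vs 25% | 23% | 4.9% |
| 50% | 60% vs 50% | 12% | 5.2% |
| 75% | 80% vs 75% | 7% | 4.9% |

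Hand check of the first row. With no control events, 3 AG-920 events give 0.0100/0.00317 = 3.16 (not significant) and 4 give 0.0178/0.00415 = 4.29 (significant). Power is therefore the chance of at least 4 events in 30 at 20%, which is 0.877.

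With no drug effect, shares of 25%, 50% and 75% give 7.5, 15 and 22.5 abnormal children expected in each arm (30 × *d*).

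**4. Unequal drop use, no drug effect.** Drop-induced abnormality of 60% against 40% gives P < 0.05 in 35% of trials; 50% against 25% gives it in 52%. Protocol 3.5 masks only the subject and the parent or guardian, so the person running the exam can know the assignment.

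**The case against.** The strongest reply is that the premise is assumed. No dilating or focus-relaxing drop is mentioned anywhere, the named agents are fluorescein and local anesthetic, and the redacted prohibited list may exclude what matters. This stands: the pupil and acuity part is conditional, and the illustration is not a forecast.

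Second, waiving individual documentation does not forbid it. Protocol 6.4.3.2 still asks about changes in medication, and Table 1 has a medication query at Visit 2. This also stands, but a general query does not cancel a specific exemption, so a complete record cannot be relied on.

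Third, randomization protects the comparison. With equal use it does, as the error rates near 5% show. A chance imbalance is already covered by the test's nominal level; a systematic false signal needs unequal use.

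Fourth, the declared secondary endpoints are adverse events and withdrawals, and acuity and the external exam are supporting parameters. This lowers the stakes without removing them, because adverse events face the same attribution problem.

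A reader might also infer that post-dose findings are tested against screening, or that the fellow eye is lost as an untreated control. The SAP supports neither. It compares arms at each time point, tabulates each eye separately, and plans no contrast between eyes.

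Finally, it is tempting to restrict the main tables to eyes with no other drop. That would condition on a choice made after randomization by an unmasked investigator. An eye given extra anesthetic because the study drug was inadequate would drop out, possibly more often in one arm. The restriction could introduce the bias it is meant to prevent.

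**Conclusion.** The point holds as a conditional attribution problem that should be fixed. The plan places its only scheduled post-dose ocular checks after an exam with permitted drops, waives the record of those drops, and has no rule for separating their effects.

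If they cause findings, rates rise in both arms and a true difference is diluted: from about 88% power to about 23% at a 25% share, for an assumed 20% versus 0% effect with 30 per arm. At a 0% share there is no effect. If use differs by arm, a false signal becomes possible and could not be recognized without a record.

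The documents do not support the stronger statement that exam-drop effects will be counted as study-drug findings, or that the tables will show high abnormality rates. The content of the exam is not given and the share is unknown.

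**What to change.** 1. In Protocol 5.1.2, remove the documentation exemption for Day 1. Record product, eye and clock time of every diagnostic drop given from dosing to the post-dose check.
2. In SAP 2.9.3 and 5.4, keep the all-subject safety-population tables (5.1.1 to 5.2.2) as the main tables. Add a supportive split by whether the eye had another drop before the check.
3. Report diagnostic drop use by arm and by eye, so that unequal use can be seen.
4. List any such drop beside each abnormal finding and each ocular adverse event.
5. Reconcile the time anchor of the checks across Protocol 6.4, 6.4.3.2 and Table 1, and SAP 2.2.

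The cost is one CRF log line per child and one supportive table split. The clinical exam does not change. If no such drops are used, the log shows that and the safety tables are stronger for it. The record has to be made on Day 1, since it cannot be reliably recovered afterwards.
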